- 7. Patients with any chronic conditions affecting the upper respiratory tract (e.g., chronic sinusitis) which in the opinion of the investigator may interfere with the study evaluation or optimal participation in the study.
- 8. Patients with a history of chronic lung diseases other than asthma, including (but not limited to) COPD, sarcoidosis, interstitial lung disease, cystic fibrosis, clinically significant bronchiectasis and active tuberculosis.
- 9. Patients with Type I diabetes or uncontrolled Type II diabetes.
- 10. Patients who have a clinically significant laboratory abnormality at Visit 101.
- 11. Use of other investigational drugs within 30 days of Visit 101 or 5 half-lives whichever is longer or until the expected pharmacodynamics effect has returned to baseline.
- 12. Patients who, either in the judgment of the investigator or the responsible Novartis personnel, have a clinically significant condition such as (but not limited to) unstable ischemic heart disease, New York Heart Association (NYHA), Class III/IV left ventricular failure arrhythmia, uncontrolled hypertension, cerebrovascular disease, psychiatric disease, neurodegenerative diseases, or other neurological disease, uncontrolled hypo- and hyperthyroidism and other autoimmune diseases, hypokalemia, hyperadrenergic state, or ophthalmologic disorder or patients with a medical condition that might compromise patient safety or compliance, interfere with evaluation, or preclude completion of the study.
- 13. Patients with a history of myocardial infarction (clinical confirmation by the study investigator required) within the previous 12 months.
- 14. Concomitant use of agents known to prolong the corrected QT (QTc) interval unless it can be permanently discontinued for the duration of study.
- 15. Patients with a history of long QT syndrome or whose QTc measured at Visit 101 (Fridericia method) is prolonged (> 450 msec for males and > 460 msec for females) and confirmed by a central assessor or inability to determine the QTcF interval (these patients should not be re-screened).
- 16. Patients who have a clinically significant ECG abnormality at Visit 101 (Start of Run-in/Baseline epoch) and/or any time prior to randomization (Visit 102), including unscheduled ECG. ECG evidence of myocardial infarction at Visit 101 (via central reader) should be clinically assessed by the study investigator with supportive documentation.

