Women are considered post-menopausal and not of child-bearing potential if they have had 12 months of natural (spontaneous) amenorrhea with an appropriate clinical profile (e.g., age appropriate, history of vasomotor symptoms) or have had surgical bilateral oophorectomy (with or without hysterectomy), total hysterectomy, or tubal ligation at least six weeks ago. In the case of oophorectomy alone, only when the reproductive status of the woman has been confirmed by follow-up hormone level assessment is she considered not of child-bearing potential.

If requested by local authorities/ethics committees, additional and more frequent pregnancy testing might be performed.

34. Use of Long Acting Muscarinic Antagonist (LAMA) within 3 months prior to Visit 1.

5 Treatment

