Short acting β_2 -agonists (SABAs) (other than Salbutamol/albuterol provided at Visit 1 for rescue medication)	Must be discontinued at Visit 1 and are not permitted during the study
Parenteral or oral corticosteroids (systemic corticosteroids are permitted for the treatment of asthma exacerbations)	Must be discontinued 4 weeks prior to Run-in (Visit 101)
Intra-muscular depot corticosteroids	Must be discontinued 3 months prior to Run-in (Visit 101)
Monoclonal Antibody: IgE inhibitors and other asthma-related biologics (i.e., omalizumab), IL-5 inhibitors (e.g., mepolizumab)	Must be discontinued 4 months prior to Run-in (Visit 101)
Xanthines	Must be discontinued 7 days prior to Run-in (Visit 101)
Systemic mast cell stabilizers (e.g., cromoglycate, nedocromil, ketotifen)	Must be discontinued 7 days prior to Run-in (Visit 101)

¹ ICS must be discontinued at Visit 101. Treatment for recorded asthma exacerbation as defined in Section 6.4.9 is allowed ONLY until the asthma exacerbation is resolved (minimum wash-out of 7 days is required before scheduling a visit including spirometry assessment).

² This table is not considered all-inclusive. Medications should be assessed for adherence to the indication and other inclusion/exclusion criteria.

Table 5-2 Prohibited Medications

Class of medication	Minimum cessation period prior to Run-in (Visit 101)
Non-potassium sparing diuretics (unless administered as a fixed-dose combination with a potassium conserving drug	7 days
Non-selective systemic β-blocking agents	7 days
Cardiac anti-arrhythmics Class Ia	7 days
Cardiac anti-arrhythmics Class III	7 days, amiodarone 3 months
Other drugs with potential to significantly prolong the QT interval	14 days or 5 half-lives, whichever is longer
Strong inhibitors of cytochrome P4503A (e.g., ketoconazole)	7 days
Tricyclic antidepressants (tetracyclics which are similar in class with regards to drug interaction are also to be excluded)	14 days
Other investigational drugs	30 days or 5 half-lives, whichever is longer
Noradrenaline reuptake inhibitors	7 days
Live attenuated vaccine	30 days

Table 5-3 Medications Allowed Under Certain Conditions

iddic 0-0 Micalcations Anonca on	aci ocitalii ooliaitiolis
Class of medication	Condition
Mucolytic agents not containing bronchodilators	If stabilized for at least 4 weeks prior to Visit 1 and throughout the trial

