## 2.2 Analysis sets

The following analysis sets are defined:

- The randomized (RAN) set will consist of all patients who were assigned a randomization number, regardless of whether or not they actually received study treatment. Patients in RAN will be analyzed according to the treatment they were randomized to. The RAN set will be used for a summary of patient disposition, demographics and baseline characteristics.
- The Full Analysis Set (FAS) will consist of all patients in the RAN set who received at least one dose of study treatment. Following the intent-to-treat principle, patients will be analyzed according to the treatment they were assigned to at randomization. The FAS will be used in the analysis of all efficacy variables.
- The Per-Protocol set (PPS) will include all patients in the FAS who did not have any major protocol deviations. The list of major protocol deviations will be available in [Appendix 6.7](#) prior database lock. Patients will be analyzed according to the treatment they received. The PPS will be used for supportive analysis of the primary analysis only.
- The Safety Set will consist of all patients who received at least one dose of study treatment including non-randomized patients who received study treatment in error. Patients will be analyzed according to the treatment they received. If patients switch double-blind treatment during the study, they will be counted and analyzed only once according to their initial treatment. The safety set will be used in the analysis of all safety variables.

•

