## **4 Change to protocol specified analyses**

Section 2.7.2 Asthma control questionnaire (ACQ) : All the analyses described for ACQ-7 has been included for ACQ-5.

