EXCL02B	Adults: who had an asthma attack or exacerbation requiring systemic steroids or hospitalization or emergency room visit between visit 1 and 102

Deviation ID	Description of Deviation
EXCL02C	Adolescents: who had an asthma attack or exacerbation requiring systemic steroids or hospitalization or emergency room visit within 6 months prior to visit 1
EXCL02D	Adolescents: who had an asthma attack or exacerbation requiring systemic steroids or hospitalization or emergency room visit within: between Visit 1 and 102
EXCL03A	History of Intubation for severe asthma attack or exacerbation
EXCL05A	Patients with respiratory tract infection or asthma worsening between Visit 1 and Visit 102
EXCL05B	Patients with respiratory tract infection or asthma worsening within: 4 weeks prior to visit 1
EXCL06A	Clinically significant oropharyngeal candidiasis at Visit 102 or earlier, with or without treatment.
EXCL07A	Patient with chronic condition affecting upper respiratory tract (eg. chronic sinusitis)
EXCL08A	Patient have a medical history of chronic lung diseases other than asthma
EXCL11A	Other investigational drugs used within 30 days of visit 1 or 5 half lives or untill return of baseline pharmacodynamic effect whichever is longer.
EXCL21A	Patient on Maintenance Immunotherapy (desensitization) for allergies less than 3 months prior to Visit 101
EXCL21B	Patient on Maintenance Immunotherapy for allergies more than 3 months prior to Visit 101 but expected to change therapy throughout the study
EXCL21C	Monoclonal antibodies: IgE inhibitors and other asthma related biologics (e.g. omalizomab) IL-5 inhibitors (e.g. mepolizomab) taken within 4 months prio to run-in 101.
EXCL23A	Patient associated with any member of study team
EXCL24A	Patient unable to use the dry powder inhalers
EXCL25A	Patient has history of alcohol or other substance abuse since last 10 years
EXCL34A	LAMA taken less than 3 months prior to Visit 101
COMD09A	Parenteral or oral corticosteroids taken within 4 weeks prior to run in 101
COMD10A	Intra-muscular depot corticosteroids taken within 3 months prior to Run in 101
COMD12A	Xanthines taken within 7 days prior to Run In 101
COMD13A	Systemic mast cell stabilizers taken within7 days prior to Run in visit 101
OTH01A	Patient not having correct run in medication (i.e. 100mcg accuhaler or 125 mcg via MDI inhaler) or dose equivalent
OTH07A	Patient took study treatment not as per protocol (i.e not inhaled the study medication)

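### Two per-protocol exclusion codes in SAP 6.7 (EXCL34A, EXCL11A) count their look-back from a different visit than the protocol criteria they implement

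*SAP*

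**What the plan says.** **LAMA.** Protocol Section 4.2, criterion 34, excludes "Use of Long Acting Muscarinic Antagonist (LAMA) within 3 months prior to Visit 1". SAP Section 6.7, code EXCL34A, takes a patient out of the PPS for "LAMA taken less than 3 months prior to Visit 101".

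**Investigational drugs.** Protocol Section 4.2, criterion 11, excludes "Use of other investigational drugs within 30 days of Visit 101 or 5 half-lives whichever is longer". It adds a third limb, until any pharmacodynamic effect has returned to baseline. Table 5-2 in Section 5.5.8 gives the same period, "30 days or 5 half-lives, whichever is longer", in a column counted back from Visit 101. SAP code EXCL11A reads "Other investigational drugs used within 30 days of visit 1 or 5 half lives", followed by the pharmacodynamic limb.

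**Use of the PPS.** SAP Section 2.2 states: "The PPS will be used for supportive analysis of the primary analysis only". SAP Section 2.5.4 gives the purpose, which is to estimate the effect in patients who followed the protocol. SAP Section 2.3.1 also tabulates protocol deviations by category.

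**Declared changes.** SAP Section 4, on departures from the protocol's analyses, has one entry: "All the analyses described for ACQ-7 has been included for ACQ-5".

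**The concern.** Each code has the same number and subject as its protocol criterion and differs in the visit from which time is counted. The visits are separate dates: Table 6-1 puts Visit 1 at Day -35 to -21 and Visit 101 at Day -21. Gaps above zero are to be expected, because Table 5-1 requires 7 days off leukotriene antagonists or xanthines, and 14 days off a once-daily LABA, before Visit 101.

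The two shifts have opposite effects. EXCL34A is looser than its criterion, so some patients who breached it would stay in the PPS. EXCL11A is stricter, so some patients who complied would be removed. No single policy of tightening or relaxing the rules explains both. At stake is whether the PPS contains the patients it is meant to contain, and whether deviation counts derived from these codes are right.

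**Working it through.** The plan gives no figure to reproduce. The check is a comparison of texts followed by date arithmetic.

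**Inputs**
- g = days from Visit 1 to Visit 101, 0 to 14 (Protocol Section 3.1 and Table 6-1).
- d = days from last use of the drug to Visit 1.
- Run-in = 21 days (Protocol Section 3.1).
- Three months = 90 days. This is an assumption: SAP 6.7 equates one month with 30 days only in code INCL04A, and I carry that over.
- A window of n days is read as fewer than n days. Counting day n as inside moves each range below by one day and leaves its width unchanged.

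**EXCL34A**
- Criterion 34 is breached if d < 90.
- EXCL34A flags if d + g < 90.
- A breach is missed if 90 - g <= d < 90, a span of g days.

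**EXCL11A, 30-day limit**
- Criterion 11 is breached if d + g < 30.
- EXCL11A flags if d < 30.
- A compliant patient is flagged if 30 - g <= d < 30, also a span of g days.
- The 30-day limit governs over the half-life limit when 5 half-lives <= 30 days, so half-life <= 30/5 = 6 days. The pharmacodynamic effect must also have returned to baseline.

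| Gap g | Breaches missed by EXCL34A | Compliant use flagged by EXCL11A |
|---|---|---|
| 0 days | 0 days | 0 days |
| 7 days | 7 days (d = 83 to 89) | 7 days (d = 23 to 29) |
| 14 days | 14 days (d = 76 to 89) | 14 days (d = 16 to 29) |

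**Examples at g = 14**
- Last LAMA at d = 80: 80 + 14 = 94 days before Visit 101. Criterion 34 is breached (80 < 90), but EXCL34A does not fire (94 >= 90).
- Last investigational drug at d = 20: 20 + 14 = 34 days before Visit 101. Criterion 11 is met (34 >= 30), but EXCL11A fires (20 < 30).

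**Possible carry-over.** A patient missed by EXCL34A has d + g >= 90, so has been off LAMA for at least 90 days at Visit 101 and about 90 + 21 = 111 days at first dose. I claim no residual effect on FEV1.

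**Are these two codes exceptional?** Twenty look-back codes in SAP 6.7 name a visit: INCL03A, INCL04A; EXCL01A, 02A, 02C, 05B, 11A, 21A, 21B, 21C, 34A; COMD02A, 03A, 04A, 05A, 06A, 09A, 10A, 12A, 13A. Against the protocol, 17 use the same visit. One (EXCL02C) implements a criterion that names no visit. Two conflict: EXCL11A and EXCL34A. The total is 17 + 1 + 2 = 20.

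**The case against.** The best defence is that the list of major deviations is the SAP's to write. Protocol Section 9.1 leaves the definition to the SAP, and the list does not mirror eligibility: criteria 9, 10, 13, 15 and 17, for example, have no PPS code. A LAMA breach that leaves the patient off drug for about 111 days before dosing could reasonably be called minor. This has force for EXCL34A, although nothing visible in the SAP says a shorter look-back was intended. It does not help EXCL11A. The PPS removes patients with major protocol deviations, and a patient who meets criterion 11 has no deviation on that point.

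Second, the entries may be short labels and not programming rules. INCL08A, for instance, omits the retest and historical evidence that criterion 8 allows. That is true, and the consequences here do depend on literal application. But an abbreviation drops detail, whereas these two codes name a different visit.

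Third, SAP Section 4 concerns changes to analyses, and the protocol specifies no deviation list. Its silence is therefore weak evidence, and the finding does not need it.

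Fourth, nothing states that the 6.7 wording drives the deviation table in SAP 2.3.1. I accept that: the effect on deviation counts is an inference.

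Finally, the practical effect is very small, and code OTH14A separately covers investigational drugs taken during the study. Both points stand and limit the importance of the finding.

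**Conclusion.** The concern holds. Both codes are wrong as written: each names a different visit from its criterion, and the shifts run in opposite directions. EXCL11A is the clearer error because it can exclude a compliant patient.

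The size is 0 to 14 days of window for each code, depending on the screening gap. These are days, not shares of patients. The documents do not allow a patient count. It is probably very small, because sites check the protocol criteria before randomization. The day ranges assume a 30-day month and literal use of the codes; the mismatch of visits assumes neither.

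The effect reaches PPS membership and possibly deviation counts. The primary and key secondary analyses on the full analysis set, alpha and power do not change. The correction is worth making but is of low priority.

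**What to change.** Reword two lines of SAP 6.7 before database lock.

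- **EXCL34A:** flag LAMA use in the 3 months before Visit 1, or at any time between Visit 1 and Visit 101. The second part goes beyond criterion 34 on purpose. It keeps the screening coverage the code has now, and the current Table 5-1 has no LAMA row to supply it. Nobody now flagged is lost, since d + g < 90 implies d < 90; the missed days are added.
- **EXCL11A:** count the 30 days from Visit 101 and follow criterion 11's structure: the longer of 30 days and five half-lives, or until the pharmacodynamic effect is back to baseline. This also moves the longer-of condition, which the SAP places after all three limbs, to where criterion 11 has it.

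If either shift was intended, a sentence giving the reason would serve instead. The protocol, Table 5-1, code COMD16A and the full-analysis-set rules need no change. The cost is two lines of text, with no new patients or data. A few patients may move into or out of the PPS.
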